6.1 Participant Screening

Inclusion Criteria

- Walking speed <0.8m/s
- Self-reported Physical activity <3 hours/week
- Hand grip strength <30 kgs for men & <20 kgs for women (this will be assessed only for participants who come for in-person assessment)
- Not on any sedative drugs
- Can understand & communicate in English
- Ability to walk more than 30 feet with or without an assistive device
- Must have either a desktop computer/laptop/tablet with access to internet (only for participants who choose to go for online assessments and/or training)Must have a helper buddy assistance (only for participants who choose to go for online assessments and/or training). The helper buddy will be asked to stay in the same room throughout the online assessment and online training sessions. The helper buddy will not participate in any other way throughout the research procedures. In case of any adverse event, we will follow the adverse event protocol. The session will be immediately concluded, and the participant will be provided all the necessary support by the helper buddy while the research personnel stays online to ensure the participant is taken care of. The participant will be asked for symptoms and the type of discomfort he/she is experiencing. The adverse event will be immediately reported to the PI and the participant will be asked to visit his physician or doctor to seek medical attention in case the symptoms persist for more than a day. In case of emergency, like chest discomfort, the helper buddy will be asked to call 911 immediately
- 2-minute step in place test or walk around: The participant is asked to stand up straight next to the wall with the heart rate/O2 monitor plugged in to the index finger. The subject then marches in place or walks around the room (with health coach able to see them on the screen) for two minutes. On completion, the health coach will obtain the heart rate and oxygen saturation. If the HR exceeds 85% of age appropriate HR max and O2 saturation falls below 90% then they will be excluded from the study.

Exclusion Criteria

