- Participants will not proceed with the study if any of the following occurs at baseline measurement: 1) HR > 85% of age-predicted maximal heart rate (HRmax) (HRmax = 220 age), 2) systolic blood pressure (SBP) > 165 mmHg and/or diastolic blood pressure (DBP) > 110 mmHg during resting), and/or 3) oxygen saturation (measured by pulse oximeter) during resting < 90% (only for participants who choose to go for inperson assessment and/or training). For The blood pressure criteria is only for participants who choose to go for in-person assessment and/or training which will be measured in laboratory (Group 1 and 2). To serve good for safety in group 3 (online assessment and online training), we will mail O₂ saturation monitors along with heart rate monitors. Participants will not proceed with the study if at baseline measurement HR > 85% of age-predicted maximal heart rate (HRmax) (HRmax = 220 age) (only for participants who choose to go for online assessments and/or training). If excluded and the participant wants to participate in the study, they would need to obtain a physician consent.
- Unable to stand for 5 minutes without an assistive device (length of a Wii Fit game)
- Uncontrolled acute medical/surgical, neurological or cardiovascular disease
- History of bone fracture or significant other systemic disease or surgery in the last six months
- Moderate to severe cognitive impairment (MOCA <24/30)
- Specific to MRI participants: Self-reported presence of pacemaker, metal implants other than orthopedic implants, and/or Claustrophobia, cataract surgery (lens not compatible to the MRI confirmed by the MRI technician)
- Do not have either a desktop computer/laptop/tablet with access to internet (only for participants who choose to go for online assessments and/or training)
- Do not have a helper buddy to assist or provide physical support (only for participants who choose to go for online assessments and/or training)
- Participants who cannot understand and communicate in English will be excluded due to instructions for training and protocol being provided in English.

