Preventing falls during training sessions: There is also a risk of balance loss and falls while participating in the actual balance training on the Wii-Fit balance board. For that reason, participants will always be made to wear gait belt and supervised by a research personnel mentioned in Appendix P during the training sessions. Blood pressure and heart rate will be monitored prior to the training session, after each sub-session (completion of 4 games). Participants will be given a chair to sit back after each subsession (completion of 4 games - approximately 10 minutes considering each game played for 1.5 minutes) or if he/she feels tired during the game (i.e., ≥ 15 on Borg scale for perceived exertion) or if the blood pressure is beyond normal limits (i.e. > 85% of age-predicted maximal heart rate). More than or equal to 15 on the Borg scale of perceived exertion indicates that the intensity of the physical activity performed was high and that it gives an idea to the research personnel that the participant would need to slow his movements down. Additionally, if at any point the heart rate, blood pressure, drops or rises above the pre-determined acceptable limits, the session will be terminated. Participants will be asked to inform the experimenter about any of the symptoms including marked breathlessness, excessive sweating, pain in chest, or fatigue. The research personnel will observe for any changes in participant's facial expression indicating anxiety or discomfort. In case of any discomfort, the session will be terminated, and the time of the training session will be noted.

Preventing injuries from training: The proposed setup incorporates several precautionary features, evolved through a decade of research, against such injuries. To further reduce the risk of injury, all Participants will undergo a series of stretching and warm-up exercises at the start of the experiment and training. A physical therapist or an exercise specialist on the team will conduct these procedures. Stretches will encompass all major muscle groups of the lower limbs and trunk. Warm-ups include activities such as walking, lunges, squats, high stepping and chair rise.

Potential Risks: Pertaining Online assessment and training

Clinical test related risks

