11.0 Data and Safety Monitoring

There will be a dual data and safety monitoring plan in place. One which is monitored by the research team itself and the second which is monitored by a Data and Safety Monitoring Board/Committee (DSMB).

The Principal Investigator (PI) [name] will be responsible for ensuring participants' safety daily. In addition, other individuals the Safety Officer in conjunction with a Data Safety Monitoring Roybal Center Committee will act in an advisory capacity to monitor participant safety, evaluate the progress of the study, to review procedures

for monitoring the confidentiality of the data, the quality of data collection matter, management, and analyses.

For monitoring participant safety during the testing and training sessions, Participants will be asked whether they are feeling any pain or any kind of distress at regular intervals. Participants' heart rate (HR), blood pressure (BP) and blood oxygen levels will be monitored before and after testing, and before, after and during training session. The experiment will be stopped if any discomfort noticed and the HR > 20 bpm of the resting HR or blood oxygen drops below 92% or systolic BP exceeds > 20 mmHg of the resting state or if the diastolic BP exceeds > 15 mmHg from the resting state. There will always be two people in the experiment area to guard the participant if required. There is always a first aid kit available in the lab for use in case of any minor injury. We also have an AED for emergencies and at least one of the investigators during any experiment will be AHA-BLS (American Heart Association - Basic Life Support) certified for health care providers. In addition, we do regular harness checks to ensure that it is not damaged. Also, the participants will be called 2 days after the testing session and will be asked to inform the research personnel if there is any discomfort during the intervention period.

Adverse Event and Serious Adverse Event Collection and Reporting

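### As written, low oxygen saturation alone never excludes a Group 3 (fully online) participant, and the in-person entry limit of 90% sits below the 92% stopping limit

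*Combined protocol and SAP*

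**What the plan says.** **In-person entry (section 6.1, Exclusion Criteria).** Any one of three baseline findings bars a participant. One is "oxygen saturation (measured by pulse oximeter) during resting < 90" per cent, and the section restricts it to people assessed or trained in person.

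**Group 3 entry (section 6.1, Exclusion Criteria).** The same bullet continues "To serve good for safety in group 3 (online assessment and online training), we will mail" oxygen monitors together with heart-rate monitors. The online criterion that follows is a heart-rate limit with no oxygen limit: "Participants will not proceed with the study if at baseline measurement HR > 85% of age-predicted maximal heart rate (HRmax". The bullet ends by allowing an excluded person to enter with physician consent.

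**Two-minute test (section 6.1, Inclusion Criteria; section 6.3, online step 2).** The participant is excluded if "HR exceeds 85% of age appropriate HR max and O2 saturation falls below 90" per cent. Section 6.3 repeats this rule for Group 3.

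**Online resting check (section 6.3, online step 1).** Resting oxygen below 90% and heart rate above 85% of maximum are again joined by *and*. The consequence is exclusion or the option of physician consent.

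**Stopping (section 11.0).** The experiment stops "if any discomfort noticed and the HR > 20 bpm of the resting HR or blood oxygen drops below 92" per cent, or if systolic or diastolic pressure rises by a set amount over rest. On timing, "blood oxygen levels will be monitored before and after testing, and before, after and during training session".

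**In-person training (section 7.0).** "if at any point the heart rate, blood pressure, drops or rises above the pre-determined acceptable limits, the session will be terminated". Also, "In case of any discomfort, the session will be terminated". Oxygen is not named in either sentence.

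**The concern.** The plan sends Group 3 participants an oximeter for safety, yet none of its written entry rules acts on an oxygen reading unless heart rate is also very high. These are frail adults aged 60 or over who exercise at home without trained staff in the room. The same reading would bar them if they came to the laboratory.

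The in-person limits raise a smaller problem. A person can satisfy the entry rule and already be under the stopping limit at the first pre-session reading. Staff then have to decide whether that person may start. The stopping sentence does not settle this, because it mixes *and* with *or*.

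What is at stake is participant safety and consistent handling across groups. No sample size, power or analysis figure depends on it.

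**Working it through.** The plan states no figure to reproduce. The check applies each written rule to the same readings.

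**1. The heart-rate condition.** Section 6.1 takes maximum heart rate as 220 minus age, so the limit is 0.85 × (220 − age).
- Age 60: 0.85 × 160 = 136 bpm
- Age 70: 0.85 × 150 = 127.5 bpm
- Age 80: 0.85 × 140 = 119 bpm

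**2. Same person, two settings.** Take, for illustration, a 70-year-old resting at 88% with a heart rate of 80 bpm.
- In person: 88 < 90, so the section 6.1 criterion is met and the person is excluded, subject to any physician consent.
- Group 3, section 6.1 exclusion list: 80 is not above 127.5, so not excluded.
- Group 3, section 6.3 step 1: this needs oxygen below 90% and heart rate above 127.5. The second condition fails, so not excluded.
- Group 3, two-minute test: the same conjunction applies. Unless heart rate after the march exceeds 127.5, not excluded, whatever the oxygen reading.

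**3. What the resting oxygen clause adds.** The people caught by section 6.3 step 1 have oxygen below 90% and heart rate above the limit. They are a subset of those with heart rate above the limit, whom section 6.1 already excludes on that ground. Added exclusions: 0. This redundancy is shown for the resting clause only, because the section 6.1 heart-rate rule refers to the baseline measurement and not expressly to a reading after the march.

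**4. All rules across a range of saturations**, with heart rate at or below the 85% limit and no rise above 20 bpm or blood-pressure trigger. Reading A of section 11.0 lets oxygen stop a session alone. Reading B requires discomfort with every item.

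| Oxygen | In-person entry | Stop, reading A | Stop, reading B, comfortable | Stop, reading B, discomfort | Group 3 excluded |
|---|---|---|---|---|---|
| 87–89% | excluded | yes | no | yes | no |
| 90–91% | admitted | yes | no | yes | no |
| 92–94% | admitted | no | no | no | no |

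The in-person overlap runs from 90% to below 92%. A comfortable participant at 91% stops under reading A and continues under reading B. Section 7.0 makes discomfort alone, and heart rate or blood pressure alone, sufficient to end in-person training. It leaves oxygen open.

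**5. Absolute or relative.** In the section 11.0 sentence the heart-rate and blood-pressure limits are changes from rest, whereas 92% is an absolute value. Because oxygen is also read before sessions, a resting 90–91% would be seen against that limit before any exercise.

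**The case against.** **The *and* is probably a slip for *or*.** This is likely right. Read literally, the resting clause has no effect, and the parallel in-person list uses *and/or*. But the conjunction appears three times, in section 6.1 and in both steps of section 6.3, and it is the text staff would follow.

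**The 90–91% overlap fails safe.** This stands. On the ordinary reading of section 11.0 the participant is stopped, so the cost is operational: someone is admitted who may not be able to train. It can also be argued that a drop below 92% means a fall during the session, since the neighbouring limits are changes from rest. The text neither says so nor rules it out. A reader might infer that the plan lets hypoxic in-person participants exercise. The documents do not support that as the ordinary reading.

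**Online sessions are not shown to lack an oxygen stop.** A reader might infer that they do, because section 6.3 has oxygen checked at the start of every session and at intervals without giving a value, and the online stops in sections 6.2 and 6.3 concern heart rate, signs and symptoms. The documents do not establish this. Section 11.0 names no group, although its laboratory details (a defibrillator, two people guarding) leave its reach uncertain. The adverse event protocol figure in section 7.0 is not reproduced in the available text and may contain a value. Section 7.0 also stops the session and discontinues Group 2 and 3 participants who show shortness of breath, excessive sweating or fatigue. One-on-one video, the heart-rate stops and the helper buddy are further safeguards.

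**Physician consent can override exclusion.** This is true online. In section 6.1 the consent sentence may cover in-person participants as well, so the in-person exclusion may not be absolute. None of this supplies a Group 3 exclusion for low oxygen.

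**Conclusion.** The Group 3 finding holds on the wording alone: at any oxygen reading, a participant whose heart rate stays at or below 85% of the age-predicted maximum meets no written oxygen-related exclusion. The resting oxygen clause contributes 0 exclusions beyond the heart-rate rule. This does not depend on how section 11.0 is read, because stopping a session is not exclusion from the study.

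The in-person mismatch, 90% to below 92%, is real but minor. It rests on 92% being an absolute limit applied to pre-session readings, which is the ordinary reading. Whether oxygen alone stops a session is ambiguous as drafted.

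Whether online sessions have an oxygen stop value is a question to confirm and not a demonstrated gap. How many participants would have such saturations cannot be computed from the documents. The point should be fixed, since the rule gives the wrong result if followed and correcting it is cheap.

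**What to change.** 1. **Group 3 entry.** State in section 6.1 (both the two-minute test and the exclusion list) and in section 6.3 that oxygen below 90% is sufficient on its own to exclude a Group 3 participant, both at rest (keeping the existing physician-consent option) and after the two-minute test. In section 6.3 step 1, change *and* to *or*.
2. **Post-march rules.** Do not simply substitute *or*. That would also exclude on post-march heart rate alone, and step 2 offers no physician-consent route of its own. Make oxygen sufficient alone, and let the investigator decide whether post-march heart rate above 85% of maximum excludes or only stops the session, as section 6.3 already provides.
3. **Section 11.0.** Reword so that the oxygen limit is a sufficient stop by itself. Align it with entry, either by setting the resting entry limit no lower than the stop limit or by defining the stop as a fall from rest. The investigator and Safety Officer should choose the values.
4. **Online sessions.** Confirm that the section 11.0 oxygen limit applies to them, unless the adverse event protocol figure already gives a value.

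The cost is a wording amendment. Oximeters are already mailed, so no equipment is added. A few more people with low resting or post-march saturation may be excluded or need physician consent. That number cannot be estimated from the documents.

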An adverse event is defined as an undesirable and unintended result of therapy, intervention or interaction experienced by a participant in a research study. We will monitor adverse events, reports by participants during the intervention and maintenance phases of the study and reasons for drop out. All field staff who work directly with participants will be required to notify the PIs of any unanticipated problems/adverse events immediately upon discovery. If an adverse event is recorded during the intervention session, the session will be concluded, and the event reported to their physician and to the investigators.

Participants who report the event and will notify the University IRB. The PIs will immediately notify the Data Safety Monitoring Board and the University Institutional Review Board.

The relationship of the adverse event as not related, possibly related or definitely related will be determined using standard criteria for clinical trials and any additional guidelines used/ developed by the Data Safety Monitoring Board and the University Institutional Review Board.

Possible - to qualify, the adverse event must meet 2 of the following conditions:

- 1) Has a reasonable temporal relationship to the intervention,
- 2) Could not readily have been produced by the Participant's clinical state,

- 3) Could not readily have been due to environmental or other interventions,
- 4) Follows a known pattern of response to intervention,
- 5) Disappears or decreases with reduction in cessation of intervention.

Probable - to qualify, the adverse event must meet 3 of the following conditions:

- 1) Has a reasonable temporal relationship to the intervention,
- 2) Could not readily have been produced by the Participant's clinical state,
- 3) Could not readily have been due to environmental or other interventions,
- 4) Follows a known pattern of response to intervention
- 5) Disappears or decreases with reduction in cessation of intervention.

Definite - to qualify, the adverse event must meet at least 4 of the following conditions:

- 1) Has a reasonable temporal relationship to the intervention,
- 2) Could not readily have been produced by the Participant's clinical state,
- 3) Could not readily have been due to environmental or other interventions,
- 4) Follows a known pattern of response to intervention,
- 5) Disappears or decreases with reduction in cessation of intervention

Protection against Study Risks.

Informed Consent Process.

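### The adverse event definition presupposes causation, which conflicts with the plan's own later step of classing adverse events as not related

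*Combined protocol and SAP*

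**What the plan says.** Section 11.0 contains the only definition in the readable text, at the start of its part on safety events: "An adverse event is defined as an undesirable and unintended result of therapy, intervention or interaction experienced by a participant in a research study".

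The same part of Section 11.0 sets the reporting duty: "All field staff who work directly with participants will be required to notify the PIs of any unanticipated problems/adverse events immediately upon discovery". It then adds a causality step: "The relationship of the adverse event as not related, possibly related or definitely related will be determined using standard criteria for clinical trials". Five conditions follow, and the lowest related class is introduced by "Possible - to qualify, the adverse event must meet 2 of the following conditions"; three are needed for probable and at least four for definite.

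Serious adverse events appear later in Section 11.0, under the frequency of monitoring reports. The principal investigator is to be told as they occur and must inform the safety officer within 24 hours. No separate definition is given.

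Some routes to safety information carry no causal condition. Section 11.0 says "We will monitor adverse events, reports by participants during the intervention and maintenance phases of the study and reasons for drop out" and, for sessions, "Participants will be asked whether they are feeling any pain or any kind of distress at regular intervals". It also provides a telephone call two days after testing, at which participants are asked to tell staff of discomfort during the intervention period. Section 13.3 sends unanticipated problems to the IRB.

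**The concern.** A safety definition normally separates two questions: did something untoward happen, and was it caused by the study? Here the second question is built into the first. Whoever decides whether an occurrence meets the definition has already had to take a view on cause, before the formal criteria are reached.

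This matters because of who takes part and what the training is for. Participants are frail adults aged 60 or over (Section 4.0), and Section 7.0 expects the training to lower fall risk. Falls between sessions are thus an obvious event to watch. Table 1 in Section 6.4 lists no falls outcome, and a questionnaire on falls is mentioned only among the risks in Sections 7.0 and 11.0. Adverse event reporting is therefore the main formal place for such falls to appear. The staff who would first hear of them include trainers who work one-to-one and know which programme they deliver.

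At stake is whether the adverse event information reaching the safety officer, the monitoring committee and the IRB is complete enough for their purpose.

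**Working it through.** The plan states no figure on this point, so the check sets the rules side by side.

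**Step 1. The definition against the relatedness scale.** The definition admits only results of therapy, intervention or interaction. The scale is applied to events already called adverse events and allows the answer not related. With five conditions, each met or not met, there are 2^5 = 32 possible patterns:

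| Conditions met | Patterns | Class |
|---|---|---|
| 0 or 1 | 1 + 5 = 6 | below possible |
| exactly 2 | 10 | possible |
| exactly 3 | 10 | probable |
| 4 or 5 | 5 + 1 = 6 | definite |

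The total is 6 + 10 + 10 + 6 = 32. The protocol gives no explicit rule for not related. Reading it as anything below possible, 6 of the 32 patterns belong there. This counts patterns and says nothing about how often they occur, but it shows that the scale expects events which the definition, taken literally, does not admit.

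**Step 2. Three example events under the literal definition.**
- Muscle soreness after a session: a result of the intervention, so an adverse event.
- A fall at home on a day without training, not attributed to training: need not be classed as an adverse event.
- A hospital visit for a respiratory infection, not attributed to any intervention: need not be classed as an adverse event.

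The relatedness step implies that all three should be recorded, and that the last two might then be judged not related.

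**Step 3. Serious events.** With no separate definition, a serious adverse event is an adverse event that is also serious. The causal condition carries over, and with it the entry condition for the 24-hour notice.

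**Step 4. Whether the other routes close the gap.**
- Enquiry about pain and distress belongs to testing and training sessions. Section 6.0 schedules three training sessions a week in Group A and one in Group B. If sessions fall on separate days, 7 - 3 = 4 and 7 - 1 = 6 days a week have no session.
- The telephone call follows testing sessions, not training sessions.
- Participant reports and dropout reasons are monitored, but no rule passes them to relatedness assessment or to the committee.
- Staff must report unanticipated problems, but the term is not defined in the readable text. A fall in a frail adult could be regarded as anticipated.

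Each route can catch some events. None guarantees that an unattributed event reaches the causality criteria.

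**The case against.** The strongest reply is that this is loose drafting with little practical effect. A formal relatedness assessment after capture shows that the authors meant unrelated events to be included. No sentence tells field staff to judge cause before reporting; the duty is to "notify the PIs of any unanticipated problems/adverse events immediately upon discovery", which is wider than adverse events alone. Participant reports, dropout reasons and symptom enquiries are also free of any causal test.

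Much of this stands, and it rules out three stronger readings that a reader might infer.

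- **That unattributed events are never recorded or never reach the investigator.** The routes just listed can capture them. The text supports only that such events need not be recorded or reported as adverse events.
- **That the not related class must be empty.** The definition is not limited to the study's own therapy, so a result of some other treatment could qualify and still be unrelated to the intervention. An event first logged as an adverse event could also later meet none or one of the five conditions. The two rules are inconsistent, but the class is not logically empty.
- **That a planned safety comparison between Groups A and B is biased by a calculable amount.** Section 12.0 plans ANCOVA on balance, cognitive, gait and cardiovascular measures, and Section 11.0 plans safety reports twice a year. Neither specifies a comparison of adverse event rates between arms. Any percentage of missed events would be an assumption with no support in the documents.

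What the reply does not do is remove the conflict. The authors' intention has to be inferred from the relatedness step, against the words of the definition. Figure 2 in Section 7.0 may hold an operational capture rule that settles the matter, but it is not shown.

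**Conclusion.** The point holds as an internal inconsistency in Section 11.0. The definition presupposes causation, the relatedness step presupposes that causation is still open, and no readable section gives a definition free of attribution. As written, an event not attributed to an intervention may be left out of adverse event reporting, and a serious one may miss the 24-hour notice.

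Its size cannot be put as a number. It affects the completeness of safety counts reviewed twice a year, not the efficacy analysis. The conclusion assumes that staff apply the definition literally and that Figure 2 does not override it. If either assumption fails, the practical effect shrinks, but the wording still needs correction. The change should be made, because it is cheap and safety review depends on it.

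**What to change.** In Section 11.0, replace the definition with wording such as: *any undesirable or unintended event in a participant from consent to the end of participation, including any maintenance phase, whether or not it is thought related to the intervention*. Require staff to report all such events, including those learned of through participant reports, dropout reasons, symptom enquiries or telephone calls. Assign relatedness only afterwards, with the existing five conditions. State that serious adverse events follow the same definition with respect to cause.

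The collection window should be explicit: Section 11.0 refers to a maintenance phase, but the schedules in Section 6.0 end at the post-test (week 8 for Group A, week 10 for Group B). Figure 2 should be checked and aligned. The same edit could add probable to the sentence listing the relatedness classes, which omits it although criteria are given.

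The cost is a short change to Section 11.0, a matching field on the event form, and more events to log and review among the 120 planned participants.
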